7.0 CONCOMITANT THERAPY

7.1 Allowed concomitant therapy

Patients should receive full supportive care during study participation, including hematopoietic growth factors, transfusion of blood products, fluid and electrolyte replacement, and antibiotics when appropriate.

7.2 Excluded concomitant therapy

Use of the following therapies is prohibited during the study:

- Cytotoxic chemotherapy
- Immunotherapy (outside of this study)
- Radiotherapy (Note: Localized radiotherapy to an area not compromising bone marrow function is allowed), provided this is being performed for treatment of another malignancy. If radiotherapy is performed for progressive Richter Transformation, the patient should be removed from the study.
- Any therapies intended for the treatment of lymphoma/leukemia whether FDA-approved or experimental (outside of this study)
- Steroid therapy for anti-neoplastic intent, after initiation of blinatumomab. Inhaled steroids for asthma, topical steroids, steroids as part of premedication for blinatumomab or management of blinatumomab toxicity, or replacement/stress corticosteroids are permitted.

7.3 Recommended anti-infective prophylaxis

- Pneumocystis pneumonia prophylaxis with co-trimoxazole 160/800mg twice daily on Mondays, Wednesdays and Fridays. Patients with hypersensitivity to co-trimoxazole may receive alternative prophylaxis, per investigator discretion.
- Varicella Zoster prophylaxis with valacyclovir 500mg daily, or equivalent.
- Anti-fungal prophylaxis may be given, per investigator discretion.

7.4 Tumor lysis syndrome prophylaxis

- All patients will receive allopurinol 300mg per day for the first 16 days of cycle 1, unless contraindicated. If the patient has a contraindication to allopurinol, a suitable alternative will be chosen.
- Rasburicase may be given in high risk patients, per institutional guidelines.

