4.0 TREATMENT PLAN

This is a single arm, open label, phase II study of ibrutinib, nivolumab and blinatumomab in patients with RT.

[figure not shown]

Figure 4. Schematic of treatment plan

Patients will receive treatment as follows:

1. 2 cycles of 3 drug combination (ibrutinib, nivolumab and blinatumomab). These cycles will be 8 weeks each.
2. 9 cycles of 2 drug combination (ibrutinib and nivolumab). These cycles will be 4 weeks each.
3. Maintenance treatment with ibrutinib monotherapy until disease progression following completion of nivolumab.

4.1 Ibrutinib therapy.

Ibrutinib treatment will commence on cycle 1, day 1 at 420mg/d. Dose reductions to 280mg/d or 140mg/d are allowed per treating physician discretion, but the reason must be documented in the medical record. Ibrutinib will be given continuously until disease progression or toxicity.

4.2 Nivolumab therapy.

Patients will receive nivolumab for up to a total of 52 weeks. Dosing will be 240mg IV every 2 weeks, commencing on day 1 until 2nd response assessment, then 480mg IV every 4 weeks.

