4.3 Blinatumomab therapy

Patients will receive blinatumomab as a continuous IV infusion, commencing on day 15 of cycle 1 and day 1 of cycle 2, for 2 courses of 4 weeks each separated by a 2 week blinatumomab treatment-free interval.

In cycle 1 and cycle 2 of blinatumomab, dexamethasone pre-medication will be given as outlined in table 1, below.

Table 1. Dexamethasone treatment during the study

Treatment phase	Target patient	Dexamethasone dose
Screening	Patients with bulky or rapidly-progressive disease	Dose and duration at the discretion of the investigator
Pre-dose dexamethasone before cycle 1 and 2 of blinatumomab and before dose-escalation	All patients (before each blinatumomab cycle and dose increase)	Dexamethasone 20 mg IV/PO 12-24 hours prior to and within 1 hour before start of blinatumomab treatment in each treatment cycle, and before dose increase
During cycle 1 and 2 for the first 48 hours of blinatumomab and after each dose escalation	All patients, for the first 48 hours of each treatment cycle	Dexamethasone 8mg IV/PO Q8 hours for 48 hours.
Infusion interruption/dose modification due to adverse event	Patients who interrupt treatment > 4 hours	Dexamethasone 20 mg IV/PO 12-24 hours prior to and within 1 hour before re-start of blinatumomab treatment
In case of signs of cytokine release (CRS) of grade ≥2 (see Appendix C for grading of CRS and Appendix D for definition of high dose vasopressors)*	Patients with signs of CRS	Principal Investigator must be notified. Dexamethasone IV/PO at a dose of at least 24mg per day. The dose should then be reduced step-wise over approximately 4 days, provided signs of CRS have

		improved/resolved.
In case of CNS event grade ≥ 2 (See Appendix E for grading)*	Patients with CNS-related AE	Principal Investigator must be notified. Dexamethasone should be administered at a dose of at least 24mg/day. Dexamethasone should be reduced step-wise over approximately 4 days, provided neurological toxicity has improved/resolved.

*Please note that when dexamethasone is given for the management of toxicity, the above dexamethasone doses are a guideline. Management of dexamethasone dosing should be individualized according to the severity of toxicity and the patient's response. This management should be at the investigator's discretion.

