In cycle 1 of blinatumomab, patients will be hospitalized on day 15-31 (for the first 17 days of blinatumomab therapy). To mitigate for potential CRS and CNS events associated with introduction of blinatumomab, in cycle 1, blinatumomab will be initiated at 9mcg/day from day 15-21, followed by 28 mcg/day from day 22-28. This will be followed by 112 mcg/day from day 29-42. In cycle 2, patients will be admitted for the first 3 days. Blinatumomab in cycle 2 will be administered at a dose of 112 mcg/day from day 1-28.

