5.1.3 Inpatient admission

As described above, patients receiving blinatumomab may experience a spectrum of neurologic and psychiatric events, such as seizure, encephalopathy, tremor, apraxia, speech disorders (dysarthria, aphasia) and disorientation. The incidence of patients experiencing neurologic and psychiatric events is greatest within the first few days of initiating blinatumomab therapy and on dose escalation. Reversible, grade 3 neurotoxicity was seen in 6 of 21 patients (26%) receiving blinatumomab for DLBCL, given at the same dose and schedule as will be used in this study. As such, patients will be hospitalized for the first 17 days of cycle 1 and 3 days of cycle 2 as outlined in section 5.1.6 and if dose interruption of >4 hours occurs during outpatient therapy. In addition, cytokine release syndrome (CRS) and/or tumor lysis syndrome (TLS) may occur on initiation of therapy, particularly in patients with high tumor load. Patients will receive IV hydration and allopurinol for tumor lysis syndrome

prophylaxis. Rasburicase will be given if indicated, according to institutional guidelines. Allopurinol (or equivalent, in the case of allergy) will be continued for the duration of hospitalization. Patients will be discharged after 17 days, provided no significant AEs requiring blinatumomab interruption and/or dose reduction have occurred.

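### Sections 7.4 and 5.1.3 give different allopurinol periods for tumor lysis prophylaxis, and the day from which 7.4 counts cycle 1 is not defined

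*Combined protocol and SAP*

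**What the plan says.** Two sections set an allopurinol period.

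- Section 7.4 (Tumor lysis syndrome prophylaxis): "All patients will receive allopurinol 300mg per day for the first 16 days of cycle 1, unless contraindicated".
- Section 5.1.3 (Inpatient admission): "Allopurinol (or equivalent, in the case of allergy) will be continued for the duration of hospitalization".

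The calendar for both comes from section 4.

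- Section 4.0 describes "2 cycles of 3 drug combination (ibrutinib, nivolumab and blinatumomab). These cycles will be 8 weeks each", and section 4.1 starts ibrutinib on day 1 of cycle 1.
- Section 4.3 has blinatumomab "commencing on day 15 of cycle 1 and day 1 of cycle 2".
- For the dose steps, section 4.3 says "blinatumomab will be initiated at 9mcg/day from day 15-21, followed by 28 mcg/day from day 22-28" and then "This will be followed by 112 mcg/day from day 29-42".
- For the stay, section 4.3 says "patients will be hospitalized on day 15-31 (for the first 17 days of blinatumomab therapy". Table 4, footnote 3 (section 9.0) repeats days 15-31.

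Sections 5.1.3 and 5.1.6 describe the same stay as the opening 17 days of cycle 1. That agrees with section 4.3 only if cycle 1 is counted there from the first day of blinatumomab.

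**The concern.** A reader who takes 7.4 at face value and uses the section 4 calendar would end allopurinol on day 16, the second day of blinatumomab. A reader of 5.1.3 would continue it until discharge, planned for day 31. Neither section refers to the other, and nothing says which prevails.

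This is a safety measure meant for every patient unless contraindicated. Section 5.1.2.4 states that tumor lysis on blinatumomab can be fatal, and section 5.1.3 places the risk at the start of therapy. Table 4, footnote 10 requires at least daily uric acid, calcium and phosphorus on the day of each dose initiation or escalation and for two days after. Only 7.4 gives both an allopurinol dose and a day count, so it is a natural source for someone writing orders. Two sites, or two physicians at one site, could each follow the protocol and give different prophylaxis.

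**Working it through.** The check is a day count on the cycle 1 calendar. No power, alpha or boundary formula is involved. It assumes the planned schedule with no interruption of blinatumomab.

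**Inputs**

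| Item | Days of cycle 1 (section 4 calendar) | Source |
|---|---|---|
| Start of cycle 1 (ibrutinib) | 1 | 4.1 |
| Start of blinatumomab | 15 | 4.3 |
| Step to 28 mcg/day | 22 | 4.3 |
| Step to 112 mcg/day | 29 | 4.3 |
| Planned stay | 15-31 | 4.3; Table 4, footnote 3 |
| Allopurinol, 7.4 | first 16 days of cycle 1 | 7.4 |
| Allopurinol, 5.1.3 | the stay | 5.1.3 |

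**Reproducing the plan's own figures**

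- Length of stay: 31 − 15 + 1 = 17 days, as section 4.3 states.
- Blinatumomab days: 7 + 7 + 14 = 28, and 42 − 15 + 1 = 28, which matches the 4-week course.

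The section 4 calendar is therefore consistent with itself.

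**Reading A: cycle 1 in 7.4 counted from ibrutinib day 1**

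- 7.4 period: days 1-16.
- Overlap with blinatumomab: days 15 and 16, which is 2 of 28 infusion days.
- Overlap with the stay: 2 of 17 days. Days 17-31 (31 − 17 + 1 = 15 days) fall under 5.1.3 but not 7.4.
- Difference in end dates: 31 − 16 = 15 days.
- Gap from the end of the 7.4 period to the dose steps: 22 − 16 = 6 days and 29 − 16 = 13 days.

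**Reading B: cycle 1 in 7.4 counted from blinatumomab day 1, as in 5.1.3 and 5.1.6**

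- 7.4 period: day 15 to day 15 + 16 − 1 = 30.
- Both dose steps (days 22 and 29) fall inside it.
- Difference in end dates: 31 − 30 = 1 day.
- 7.4 states no period for days 1-14, when ibrutinib is already being given. Section 5.3.9 links ibrutinib to tumor lysis as well.

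**Side by side**

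| | 7.4, reading A | 7.4, reading B | 5.1.3 |
|---|---|---|---|
| Period | 1-16 | 15-30 | 15-31 |
| Day 15 (start) | inside | inside | inside |
| Day 22 (step) | outside | inside | inside |
| Day 29 (step) | outside | inside | inside |
| End date short of 5.1.3 by | 15 days | 1 day | – |

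The periods differ under both readings. The two readings of 7.4 also lie 14 days apart (30 − 16).

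Interruptions can change these figures. Section 6.1.4 keeps interrupted patients in hospital during re-escalation and does not number missed days as treatment days. The 5.1.3 period would lengthen with the stay, while the 7.4 period is a fixed count.

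**The case against.** The strongest answer is that the protocol as a whole does provide allopurinol over both dose steps. Section 5.1.3 runs it through the stay, and days 22 and 29 lie within days 15-31. This stands. A reader might infer from 7.4 that the escalations are left without prophylaxis, but the documents do not support that. The steps fall outside the period only if 7.4 is followed alone and on reading A.

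The second answer is that reading B may be what was meant. Sections 5.1.3 and 5.1.6 already use cycle 1 in that sense. A 16-day count also fits it: the steps fall on blinatumomab days 8 (22 − 15 + 1) and 15 (29 − 15 + 1), both within 16 days. This also stands as a possibility. But section 4 defines cycle 1 as the three-drug cycle starting with ibrutinib, and 7.4 sits in the general concomitant-therapy section rather than under blinatumomab. The text does not decide between the readings, and reading B still leaves a one-day mismatch and no stated period for days 1-14.

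Third, the two passages might be read as cumulative. Section 5.1.3 speaks of continuing allopurinol, which presupposes an earlier start, and 7.4 does not say that it must stop. On that view 7.4 starts it and 5.1.3 extends it to discharge. This is possible, but neither section says so.

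Three further limits on the point are fair. The documents do not say that 7.4 overrides 5.1.3 because of its title. They do not attribute tumor lysis risk specifically to escalation; they only schedule laboratory tests around it. Allopurinol is also not the only measure, since 5.1.3 adds intravenous hydration, and both sections provide for rasburicase in some patients.

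**Conclusion.** The point holds as an internal contradiction with an undefined day-count origin. The 7.4 and 5.1.3 end dates differ by 15 days if cycle 1 in 7.4 starts with ibrutinib, and by 1 day if it starts with blinatumomab. Only the first reading puts the day 22 and day 29 steps beyond the 7.4 period, by 6 and 13 days, and 5.1.3 covers them even then. The figures rest on the planned section 4.3 calendar without interruptions.

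It would go too far to say that prophylaxis is missing at the dose steps, or that every enrolled patient would be affected. The wording applies to each of up to 21 combination-phase patients, but the effect depends on which section is followed, and the trial may stop before 21.

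The point does not touch sample size, the stopping boundaries or the operating characteristics. Tumor lysis is not named in the section 14.0 toxicity definition used for monitoring. The text should still be corrected, because it governs a safety measure for the whole cohort.

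**What to change.** Reconcile sections 7.4, 5.1.3 and 4.3 so that a single allopurinol period appears in the same terms in 7.4 and 5.1.3. State the day from which it is counted (cycle 1 day 1 or the first day of blinatumomab), and whether the period moves with the stay when blinatumomab is interrupted. If cycle 1 is to keep two meanings, define each one, and align the length-of-stay wording in 5.1.3 and 5.1.6 with the day 15-31 wording in 4.3. Which period applies is for the sponsor to decide.

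The cost is a wording amendment. No analysis, sample size or monitoring boundary changes.

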8.0 PRE-TREATMENT EVALUATION

Pre-treatment evaluation is outlined in table 3.

Table 3. Pre-treatment evaluation

Pre-treatment evaluation is outlined in table 3, below. Further explanation for the specific tests ordered is provided in table 4, contained within section 9.

Procedure	Schedule
Informed consent	Within 30 days of therapy
Medical history	Within 14 days of therapy
Complete physical examination including vital signs	Within 14 days of therapy
Complete neurologic exam	Within 14 days of therapy
Document concomitant medications	Within 14 days of therapy
Hematology	Within 14 days of therapy
Biochemistry	Within 14 days of therapy
Bone marrow aspirate and biopsy	Within 60 days of therapy
CLL prognostic marker evaluation on bone marrow (FISH, using probes for ATM (11q22.3), D12Z3 (12cen), D13S319 (13q14.3), LAMP1 (13q34), p53 (17p13.1); stimulated metaphase cytogenetics; next generation sequencing (NGS) panel for CLL-associated mutations, including TP53 (see below for details); IGHV mutational status and VH utilization (this does not need to be repeated if previously performed at M.D. Anderson); flow cytometry, including CD38. Please note tests can be done on peripheral blood if a bone marrow sample is not available. Additionally, some patients with Richter Transformation may not have sufficient CLL cells in bone marrow or blood to perform this testing. Not performing these tests will therefore not be considered as deviations.	Within 60 days of therapy
PETCT scan. If PETCT cannot be done for logistic reasons, CT scan of the neck, chest, abdomen and pelvis will be performed instead.	Within 28 days of therapy
Lymph node biopsy (or pathology review of recent biopsy material). If a lymph node biopsy consistent with Richter Transformation was performed outside this window and PETCT shows changes consistent with Richter Transformation, biopsy does not need to be repeated. Pathology review for out-of-window biopsies does not need to be performed if the diagnosis was made originally at M.D. Anderson.	Within 28 days of therapy
Prognostic marker evaluation on lymph node biopsy material. Where possible, this will include CLL FISH panel or array cGH, unstimulated and stimulated metaphase cytogenetics, IGHV mutational status and VH utilization and NGS panel	
Pregnancy test	Within 7 days of therapy
Immunologic evaluation, if patient consents to correlative studies	Within 14 days of therapy

Tissue banking	Within 28 days of therapy
----------------	---------------------------

9.0 EVALUATION DURING TREATMENT

Table 4: evaluation which will take place pre-treatment and during the study

Assessment	Base-line(1)	Cycle 1				Response assess	Cycle 2						Response assess	Ibrutinib + nivolumab consolidation (q4w for 36 weeks from 2 nd response assessment)	Surveillance (2)	At progression/ End-of-study
Day within cycle(3)	-28 to 1	1	15-31	36	43	57 (+/- 1 week)	1-3	8	15	22	29	43	57 (+/- 1 week)			
Informed consent(4)	X															
Medical history(5)	X	X	X	X	X	X	X	X	X	X	X	X	X	X	q12w	X
Physical examination(6)	X	X	X	X	X	X	X	X	X	X	X	X	X	X	q12w	X
Neurological examination(7)	X	X	X	X	X		X	X	X	X	X					
Concomitant medications(8)	X	X	X	X	X		X	X	X	X	X	X		X	q12w	X
CBC with differential(9)	X	X	X	X	X	X	X	X	X	X	X	X		X	q12w	X
Bio-chemistry(10)	X	X	X	X	X	X	X	X	X	X	X	X	X	X	q12w	X
Thyroid function(11)	X	q4 w														
Bone marrow(12)	X					X							X			X
PETCT scan(13)	X					X							X	q12 weeks	q24w	X
Lymph node biopsy(14)	X															X
Pregnancy test(15)	X															X
NGS panel(16)	X															X
Immunologic evaluation(17)	X															X
Tissue banking(18)	X															X
ctDNA(19)	X					X							X	At completion of nivolumab		X
Saliva (20)	X															

¹Baseline/screening testing. This must be performed within the timeframes outlined in table 3.

²Surveillance. Patients will have routine history and physical examination, CBC, routine biochemistry approximately every 12 weeks and a PETCT scan or CT scan with and without IV contrast approximately every 24 weeks (+/- 4 weeks) after completing ibrutinib + nivolumab consolidation, until 2 years after initiation of therapy, until relapse, allogeneic stem cell transplantation, or initiation of salvage therapy, whichever occurs first. Patients who have not proceeded to allogeneic

transplantation and who remain in remission at the end of the study, and those who proceed to transplant, will be enrolled on a departmental umbrella protocol (DR09-0223) to follow them for overall survival.

³Evaluations during the inpatient stay (planned for day 15-31) must take place on the scheduled day. Please note that many patients will have treatment delays, as a result of toxicity. This is expected. After hospital discharge, evaluations during cycle 1 occur weekly and can occur within +/- 4 days of the scheduled time. Response assessment must take place between 2 and 4 weeks after the completion of cycle 1 of therapy. Cycle 2 should commence 4-8 weeks after completion of cycle 1. Evaluation during cycle 2 days 1-3 (given as an inpatient) should occur on the scheduled day. Subsequent evaluations during cycle 2 can occur within +/- 4 days of the scheduled time. Subsequent response assessment must take place between 2 and 4 weeks after the completion of cycle 2 of therapy. Please note that response assessments should take place on day 57 of cycle 1 and cycle 2 (+/- 1 week). Cycle 2 will not commence, until after completion of the first response assessment.

⁴Informed consent. All patients must take part in the informed consent process. During the consent process, the person obtaining consent must inform the patient of all elements of informed consent. Adequate time must be allowed for questions and for the patient to make a voluntary decision. No protocol-specific procedures are to be performed until the patient has signed and dated an Institutional Review Board (IRB)/Ethics Committee (EC)-approved informed consent form. Each patient's participation in the trial begins with the signing and dating of the informed consent form.

⁵Medical history. Medical and surgical history and demographic information will be recorded at baseline. Medical and surgical history includes diagnoses, therapies, and medical and surgical treatments. Particular attention should be paid to any pre-existing neurological symptoms. At subsequent assessments, focused history/AE assessment will be performed.

⁶Physical examination, including vital signs. Vital signs are temperature, pulse, respiratory rate, and blood pressure. A complete physical examination, including measurement of weight, must be performed at screening; at Cycle 1, Day 1 prior to the first administration of study drug and at the end-of-treatment Visit. Height need only be recorded at the initial visit. Following the physical examination for Cycle 1, Day 1 — with the exception of the end-of-treatment Visit, where a full physical

examination must also be performed — all subsequent physical examinations, can be focused to the individual needs of the individual patient.

⁷A neurological examination must be performed during the screening period. Neurological examination at the screening assessment should include examination of the peripheral nervous system, cranial nerves and cognitive function. The latter must be determined using The M.D. Anderson simplified 10 point neurologic examination. Subsequent to the screening exam, the neurological assessment can be tailored, according to the patient's symptoms. Whenever there is a change in neurological status suggestive of blinatumomab-related neurotoxicity, the M.D. Anderson 10 point neurological examination score will be documented, to assist toxicity grading (see Appendix E and G).

⁸Concomitant medications. These will be captured in the medical record.

⁹Complete blood count with differential.

¹⁰Biochemistry. At screening, at a minimum this should include the following: sodium, potassium, chloride, bicarbonate (or total carbon dioxide [CO₂]), blood urea nitrogen (BUN, or urea), random glucose, albumin, creatinine, total bilirubin (direct and indirect), ALT +/- AST, alkaline phosphatase, phosphorous, calcium, uric acid and LDH. At subsequent timepoints, this should include, at a minimum, creatinine, potassium and ALT. On the day of and for two days after dose initiation or dose escalation, uric acid, calcium and phosphorous should be measured at least daily.

¹¹Thyroid function (at least TSH and T4) is required at baseline and approximately every 4 weeks during the study to monitor for nivolumab-induced hypothyroidism, until the completion of nivolumab therapy.

¹²Bone marrow examination Bone marrow aspiration and trephine biopsy will be performed pre-treatment for cytological and histological assessment during the screening period. The following additional studies will be performed on the pre-treatment bone marrow and on bone marrow evaluation performed at disease progression: CLL prognostic marker evaluation on bone marrow (or blood if bone marrow not available): FISH, using probes for ATM (11q22.3), D12Z3 (12cen), D13S319 (13q14.3), LAMP1 (13q34), p53 (17p13.1); stimulated metaphase cytogenetics; next

generation sequencing (NGS) panel for CLL-associated mutations, including *TP53* (see below for details); *IGHV* mutational status and VH utilization (this does not need to be repeated if previously performed at M.D. Anderson); flow cytometry. Some patients with Richter Transformation may not have sufficient CLL cells in bone marrow or blood to perform this testing. Not performing the CLL prognostic factor evaluations outlined above will therefore not be considered as protocol deviations, Bone marrow evaluation for response assessment will include aspirate and biopsy for cytological and histological assessment and a standard 4-color flow cytometry panel for evaluation of minimal residual disease (MRD) in the co-existing CLL.

¹³18-FDG PETCT scan, from the head to mid-thigh, will be performed during the screening period, for response assessment, during surveillance and at disease progression. Target lesions will be evaluated by a trained radiologist: bi-directional lymph node measurements will be performed and quantitation of 18-FDG uptake in target lesions, using standardized uptake values (SUV). If PETCT cannot be done for any reason, CT will be performed instead. If CT scan was done for initial staging purposes rather than PETCT, CT scan will also be performed for restaging and surveillance.

¹⁴Lymph node biopsy may be performed. This is at treating physician discretion. The site for biopsy will be chosen according to the PETCT. The target lymph node for biopsy should have a maximal diameter of $\geq 1.5\text{cm}$ and a SUV of at least 5. An SUV of ≥ 10 is preferred for the biopsy. The investigator, in consultation with the proceduralist, who will perform the biopsy, will determine the optimal lymph node for biopsy. A surgical excisional biopsy is preferred, but if not feasible for technical or logistic reasons, a core biopsy, performed in interventional radiology, will be performed instead. If a diagnosis of RT has already been made from lymph node or bone marrow biopsy, patients need not have a repeat biopsy – however, the pathology will be reviewed at MD Anderson for diagnostic accuracy prior to the patient being considered eligible for the study. Patients will be asked for consent to store lymph node tissue for research purposes, on a separate protocol, prior to a diagnostic biopsy being performed. Lymph node biopsy will be performed during the pre-treatment screening period and at relapse.

¹⁵Pregnancy test. The pregnancy test must be a beta-human chorionic gonadotropin (β -HCG) test, using either urine or serum. Women who are not of childbearing potential (status post-hysterectomy, status post-bilateral oophorectomy, or postmenopausal [defined as amenorrhea for at least 12

months]) do not need to have the test performed. If the test is deemed necessary, it must be performed within 7 days of treatment initiation and known to be negative prior to treatment initiation. Women of childbearing potential at study commencement must also complete the pregnancy test at the End-of-Treatment Visit.

¹⁶A targeted next generation sequencing panel will be performed to identify important driver mutations in CLL and RT. The panel will be performed during the pre-treatment screening period and at relapse.

¹⁷Exploratory immunologic investigation will be performed. This will be optional and patients consented separately on protocol PA16-0360.

¹⁸Patients will be asked to have tumor tissue stored in a sample bank for later exploratory genomic analyses, on a separate IRB protocol (PA15-0965). This is optional and a separate informed consent process will be undertaken for these studies. These will be performed on the diagnostic specimen and relapse specimen.

¹⁹Blood samples will be taken pre-treatment, at each response assessment, at 1 year, 2 years and at disease progression for plasma and cell banking. These samples will be used to perform serial NGS (including potentially NGS and WGS), to identify gene mutations and copy number alterations in ctDNA and circulating mononuclear cells, if the patient agrees to participate in protocol PA16-0919.

²⁰Saliva collection will be done at baseline if the patient is participating in protocol PA16-0919.

